**Table 11: Metrics Used to Declare a Safety Signal in AE/SAE Review Process**

Monthly Metrics	Cross-Month Metrics

 
• 5 Adverse Events
 
• 2 Serious Adverse Events
 
• 1 Serious Adverse Event + 3 Adverse Events
 
• Steering Committee Direction
 
• DSMB Direction
 
	
 
• 3 Consecutive Adverse Events within the Same Community
 
• Consecutive Adverse Event and Serious Adverse Event
 
• Steering Committee Direction
 
• DSMB Direction
 

### **8.3.2 Time Period and Frequency for Event Assessment and Follow-Up**

The RSs will provide monthly reports of the estimated number of opioid-related overdoses from the EMS runs in each of their communities to the Data Coordinating Center (DCC). These data will be available approximately by the end of the month after a target month for the Kentucky and Ohio sites, two months after a target month for the Massachusetts site, and on a quarterly schedule from the New York site. As part of the DCC's regular processing of the data, AEs and SAEs will be determined within 9 days of the receipt of the monthly data from all communities to allow for data cleaning and validation to minimize erroneous AEs or SAEs.

#### **8.3.2.1 Adverse Event Reports to the Steering Committee**

A monthly report of AEs will be sent to the Steering Committee (SC). This report will include all AEs that have occurred since the last report. The SC will review the report and determine what actions should be taken, including ongoing AE monitoring.

#### **8.3.2.2 Adverse Event Reports to the DSMB, NIDA, and SAMHSA**

A monthly and semi-annual report of AEs will be sent to the DSMB, NIDA, and SAMHSA. This report will include all AEs that have occurred since the last report. The DSMB will recommend any additional actions it deems appropriate to the NIDA Director.

#### **8.3.2.3 Serious Adverse Event Reports and Follow-Up**

Once an SAE is identified, the DCC will email a report to the SC, NIDA, and SAMHSA within 24 hours. The SC will meet within 24 hours of notification to determine whether the SAE is related to the CTH intervention and assign it to one of three categories:

1. Definitely related to the CTH intervention

3. Possibly related to the CTH intervention
5. Unrelated to the CTH intervention

Because the CTH intervention is directed toward community coalitions, it is unlikely that SAEs will be related to the CTH intervention. The DSMB will be notified within 24 hours of the SC determination. If the SC determines the SAE is related to the CTH intervention, the IRB will be notified within 24 hours. The IRB or the DSMB may request additional information or recommend actions for the SC to take.

If the SC determines that follow-up action is needed, then the course of action will depend on whether the affected community is in Wave 1 or Wave 2. When a community is participating in the CTH intervention, it will incorporate this new information into the implementation of the CTH intervention (e.g., coalition members will be notified). When a community is *not* participating in the CTH intervention, it will be informed of the SAE and may elect to address the event without facilitation from the HCS team.

## **8.4 Unanticipated Problems**

### **8.4.1 Definition of Unanticipated Problems**

This protocol uses the definition of unanticipated problems (UPs) as defined by the U.S. Department of Health and Human Services Office for Human Research Protections (OHRP). OHRP considers UPs involving risks to participants or others to include, in general, any incident, experience, or outcome that meets ***all*** the following criteria:

- Unexpected in terms of nature, severity, or frequency given (1) the research procedures that are described in the protocol-related documents, such as the IRB-approved research protocol and informed consent document; and (2) the characteristics of the participant population being studied
- Related or possibly related to participation in the research (“possibly related” means there is a reasonable possibility that the incident, experience, or outcome may have been caused by the CTH intervention)
- Suggests that the research places participants or others at a greater risk of harm (including physical, psychological, economic, or social harm) than was previously known or recognized

### **8.4.2 Unanticipated Problem Reporting**

The following steps will be used to review and report an UP:

- The contact Principal Investigators at the RSs and the DCC will be responsible for identifying any event, incident, experience, or outcome that is a potential UP.
- A potential UP will be discussed by the SC within 1 workday to determine whether it meets the criteria in Section 8.4.1, and it will be reported to the IRB (as needed), NIDA, SAMHSA, and the DSMB by the next workday.
- The procedures in Section 8.4.1 will be followed to assess a potential UP and recommend any corrective actions that might be appropriate.

- The SC will make the final determination of whether the event, incident, experience, or outcome is a UP or not.
- The findings of the SC and the associated report will be submitted to NIDA, SAMHSA, the DSMB, and the IRB (if determined to be a UP). The report will include the following:
  - A detailed description of the event, incident, experience, or outcome
  - An explanation of the basis for determining that the event, incident, experience, or outcome represents an UP or not
  - A description of any changes to the protocol or other corrective actions that have been taken or are proposed in response to the UP

#### **8.4.3 Reporting Unanticipated Problems to HCS Communities**

The HCS Communications team, in conjunction with the HCS SC and the NIDA Office of Science Policy and Communications, will be responsible for reporting UPs or AEs. The steps will include the following:

- Monitoring emerging issues
- Assessing the potential for a situation to develop into a crisis
- Identifying appropriate communications strategies and actions
- Briefing spokespeople
- Developing materials to respond to the situation
- Engaging media and community channels as necessary and appropriate
- Keeping partners and stakeholders informed of the situation
- Evaluating responses and adjusting strategies as needed

### **9. STATISTICAL CONSIDERATIONS**

#### **9.1 Statistical Hypotheses**

The HEALing Communities Study (HCS) has one primary hypothesis (H1) and three secondary hypotheses (H2, H3, H4). Compared with Wave 2 communities, we hypothesize the following:

- H1: Wave 1 communities will reduce opioid overdose deaths.
- H2: Wave 1 communities will increase naloxone distribution.
- H3: Wave 1 communities will expand utilization of buprenorphine for opioid use disorder.
- H4: Wave 1 communities will reduce high-risk opioid prescribing.

#### **9.2 Sample Size Determination**

A total of 67 clusters or communities will be randomized and analyzed in an intention-to-treat (ITT) approach based on a negative binomial regression model, as described in Section 9.4.2. Detailed as follows, this study is designed to have >99% power to detect a 40% (i.e., relative

risk 0.60) reduction in opioid overdose deaths between Wave 1 and Wave 2 communities during the 12-month period of the HCS multi-site, parallel arm, cluster randomized, wait-list controlled trial. Our calculations are based on a simulation study driven by pilot data from all 67 communities, including actual community sizes and corresponding numbers of opioid overdose deaths.

Our simulation study was conducted using 20,000 replications to ensure very small error in estimated powers (i.e., 95% confidence intervals corresponding to our calculated power are no wider than 0.011 for power  $\geq 0.80$ ). This simulation study is advantageous relative to a basic power calculation approach due to the ability to account for the high variation in community sizes, as well as its ability to adapt to the analytical approach (negative binomial regression model) that will be used. To conduct our study, actual data from these 67 communities were used to empirically drive our population assumptions.

For each community, we took the average reported number of individuals in the given community and the average number of opioid overdose deaths. A negative binomial regression model was then fit to these data to extract estimates for the marginal parameters in the regression model, as well as the dispersion parameter,  $k$ , corresponding to between-community variation as expected in cluster trials. We note that this model did not include an intervention effect, because the pilot data are reflective of control conditions, and the desired intervention effect is dictated by the assumed risk reduction for which we calculate power. Furthermore, due to the unknown influence observed community-specific baseline opioid overdose death rates have on future rates, and more importantly, in order to provide conservative power calculations (greater power will potentially be achieved in our actual analysis via a reduction in unexplained variability due to the use of the observed baseline opioid overdose death rate as a covariate in the regression model), this variable was not included as a covariate in the regression model for the simulation study. In short, we obtained a value of 0.0431 for  $k$ , and with the resulting regression parameter estimates, marginal probabilities ranged from 0.000255 to 0.000436.

To conduct our simulation study, we assume that these population parameters just described will be reflective of the true parameters for the wait-list comparison population at the time of the 12-month parallel-arm trial period. The analyses were conducted as described in Section 9.4.2, with the exception that observed baseline opioid overdose death rate for the community was not incorporated into the model as a covariate, thus providing conservative power estimates.

Table 12 provides power estimates for a variety of reductions in opioid overdose deaths for the Wave 1 and Wave 2 communities. As can be seen, we have greater than 99% power to detect a 40% (i.e., relative risk 0.60) reduction and at least 83% power for any reduction of 20% or more.

**Table 12: Power calculation for underlying reduction in risk of opioid overdose fatalities between Wave 1 and Wave 2 communities**

Intervention Effect	Relative Risk (Opioid Overdose Fatality)	Power
40%	0.60	0.999
25%	0.75	0.961
24%	0.76	0.943
23%	0.77	0.925

Intervention Effect	Relative Risk (Opioid Overdose Fatality)	Power
22%	0.78	0.899
21%	0.79	0.866
20%	0.80	0.832
19%	0.81	0.792
18%	0.82	0.748
0%	1.00	0.075

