3.3 Sample Size

A total of 67 communities were randomized and will be analyzed in an intention-to-treat (ITT) framework using a negative binomial regression model, as described in Section 6.2.1.1. As designed, this study has >99% power to detect a 40% (i.e., relative rate 0.60) reduction in the rate of opioid OD deaths during the evaluation period in Wave 1 compared to Wave 2 communities. Power was calculated by empirical simulation using pilot data from all 67 communities. This included actual community rural/urban status, community population sizes and corresponding numbers of opioid OD deaths from 2016 and 2017.

The simulation study had 20,000 replications to ensure very small error in estimated power (i.e., 95% confidence intervals (CIs) corresponding of calculated power is no wider than 0.011 for power ≥ 0.80). This simulation study is advantageous relative to a basic (closed form) power calculation approach due to the ability to account for the high variation in community sizes, as well as its ability to adapt to the analytical approach (negative binomial regression model) that will be used. To conduct the simulation study, data from the 67 HCS communities were used to empirically drive population assumptions.

For each community, we used the average reported community population and the average number of opioid OD deaths from 2016 and 2017. We fit a negative binomial regression model to these data to extract estimates for the marginal parameters in the regression model, as well as the dispersion parameter, k , corresponding to between-community variation as expected in cluster trials. We note that this model did not include an intervention effect, because the pilot data are reflective of control conditions, and the desired intervention effect is dictated by the assumed rate reduction for which we calculate power. Furthermore, due to the unknown influence the baseline rate of opioid OD deaths will have on future rates, and more importantly, in order to provide conservative power calculations (greater power will potentially be achieved in our actual analysis via a reduction in unexplained variability due to the use of the baseline rate of opioid OD deaths as a covariate in the regression model), this variable was not included as a covariate in the regression model for the simulation study. In short, we obtained a value of 0.0431 for k and, with the resulting regression parameter estimates, marginal probabilities ranged from 0.000255 to 0.000436.

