In our simulation study, we assumed that the population parameters just described were reflective of the true parameters for the Wave 2 communities during the evaluation period. The analyses were conducted as described in Section 6.2.1.1, with the exception that the baseline rate of opioid OD deaths was not incorporated into the model as a covariate, thus providing conservative power estimates.

Table 1 provides power estimates for a variety of differences in the rate of opioid OD deaths during the evaluation period between the Wave 1 and Wave 2 communities. As can be seen, we have greater than 99% power to detect a 40% (i.e., relative rate 0.60) reduction and at least 83% power for any reduction of 20% or more.

Table 1. Power calculation for underlying reduction in the rate of opioid OD deaths during the evaluation period between intervention and wait-list control arms. Empirical SE estimates were utilized. Treatment allocation was not included in the initial model to extract parameter estimates, only covariates (RS and rural/urban status). A new treatment allocation was determined within each replication, balanced within RS (KY, MA, NY, OH; except for OH which has 19 communities).

Intervention Effect	Relative Rate of Opioid OD Deaths	Power
40%	0.60	0.999
25%	0.75	0.961
24%	0.76	0.943
23%	0.77	0.925
22%	0.78	0.899
21%	0.79	0.866
20%	0.80	0.832
19%	0.81	0.792

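### The dispersion k = 0.0431 was fitted to two-year average counts but used for 12-month counts, so the printed power at reductions of about 19–25% is too high for the model simulated

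*Protocol*

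**What the plan says.** SAP 3.3 states the pilot input: for each community, "we used the average reported community population and the average number of opioid OD deaths from 2016 and 2017". Protocol 9.2 says the same without naming the years: "For each community, we took the average reported number of individuals in the given community and the average number of opioid overdose deaths". One negative binomial model was fitted to these averages, with research site and rural/urban status as covariates. The result is reported as "In short, we obtained a value of 0.0431 for" the dispersion parameter, with fitted probabilities from 0.000255 to 0.000436.

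Protocol 9.2 then carries the parameters over to the 12-month trial period: "we assume that these population parameters just described will be reflective of the true parameters for the wait-list comparison population". SAP 3.3 does likewise. Neither document describes any correction of k for the averaging.

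On the baseline death rate, Protocol 9.2 says "this variable was not included as a covariate in the regression model for the simulation study". SAP 3.3 describes the effect of that omission as "thus providing conservative power estimates". The headline result for effects smaller than the 40% target is "at least 83% power for any reduction of 20% or more". SAP 6.2.5 says that the withdrawal scenarios in its Table 3 were computed by the method of SAP 3.3.

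**The concern.** A count averaged over two years is less variable than a count for one year. If the model fitted to the average still charges it with a full year of Poisson variance, the surplus is taken out of k. The simulation then generates single-year counts with too little between-community variation, and power comes out too high.

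At stake is the statement of which effect below 40% the trial could have missed. The 83% sentence and SAP Table 3 both rest on this k. The word conservative is also affected: its only support is the omitted baseline covariate, and an understated k works in the opposite direction.

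**Working it through.** **Direction.** Let a community have annual mean μ and annual dispersion k = k_p + k_s, where k_p persists between years and k_s is specific to one year.

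- Variance of a two-year average: μ/2 + (k_p + k_s/2)μ².
- Variance assumed by the fitted model: μ + k_fit μ².
- Equating the two: k_fit ≈ k_p + k_s/2 − 1/(2μ).

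Both departures from k are downward, so averaging cannot raise the fitted value.

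**Closed-form size check.** Take the printed power of 0.832 at relative rate 0.80, with ln(1/0.80) = 0.2231 and about half of the 67 communities in each arm.

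- Two-sided 0.05: SE = 0.2231/(1.960 + 0.962) = 0.0764. Information per community = 4/(67 × 0.0764²) = 10.24. Setting μ/(1 + 0.0431μ) = 10.24 gives an effective μ of 18.3.
- If the simulated test really ran at the printed null rate of 0.075: SE = 0.0814 and μ = 14.8.

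For one community with such a mean, 1/(2μ) is 0.027–0.034, which is not small beside 0.0431. Over all communities the shortfall is less, because large communities carry more of the information about k. The simulations below put it at 0.014–0.022. With k = 0.061 and μ = 18.3, information falls to 18.3/(1 + 0.061 × 18.3) = 8.65, SE rises to 0.0831, and power is Φ(0.2231/0.0831 − 1.960) = 0.77. With μ = 14.8 and the 0.075 level it is 0.78.

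**Simulation.** The inputs were:

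- 67 communities with the site and rural/urban counts of SAP Appendix 1, and rates of 25.5–43.6 per 100,000;
- allocation redrawn within site;
- maximum-likelihood negative binomial regression, with a t test on 67 minus the number of parameters;
- 8,000 replications (Monte Carlo SE about 0.005).

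Community sizes are an assumption: lognormal with log-SD 0.6, 1.0 or 1.4, scaled so that k = 0.0431 gives about 0.83 at a 20% reduction. Annual dispersion was then set so that a fit to two-year averages returns 0.0431 on average. Case (a) has all dispersion persisting. Case (b) has 30% specific to one year. The three values in each cell are for the three size sets, with the unadjusted empirical SE.

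| | Printed | k = 0.0431 | (a) all persists | (b) 30% year-specific |
|---|---|---|---|---|
| 12-month k | 0.0431 | 0.0431 | 0.065 / 0.061 / 0.057 | 0.077 / 0.073 / 0.069 |
| 19% reduction | 0.792 | 0.787 / 0.785 / 0.796 | 0.694 / 0.707 / 0.728 | 0.661 / 0.666 / 0.682 |
| 20% reduction | 0.832 | 0.829 / 0.824 / 0.838 | 0.750 / 0.750 / 0.779 | 0.705 / 0.713 / 0.725 |
| 25% reduction | 0.961 | 0.958 / 0.957 / 0.964 | 0.913 / 0.916 / 0.928 | 0.890 / 0.886 / 0.901 |
| 40% reduction | 0.999 | – | above 0.999 | above 0.999 |
| No effect | 0.075 | 0.064 / 0.073 / 0.074 | – | – |

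The k = 0.0431 column reproduces the printed power, so Table 12 is what that k gives for single-year counts. A second simulation, with log-SD from 0.7 to 1.6, also reproduced the printed curve within 2 points. For the all-persistent case it gave k = 0.057–0.063 and power of 0.70–0.72, 0.75–0.77 and 0.915–0.924 at 19%, 20% and 25%. In its extreme case, with community effects independent between years, k is 0.113–0.128 and power at 20% is 0.56–0.57.

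**Which standard error was simulated.** The null rate of 0.075 has a Monte Carlo SE of about 0.002 at 20,000 replications, so it is clearly above 0.05. The unadjusted SE comes close to it. The average of the two small-sample corrected SEs in SAP 6.2.1 gives a null rate of 0.045 / 0.052 / 0.050. With k left at 0.0431, that adjusted SE alone gives 0.786 / 0.772 / 0.789 at 20%.

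**Planned analysis.** Adding a 12-month baseline-rate covariate and using the adjusted SE, with data generated at the single-year k, gives at 20%:

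- all of k persisting: 0.866 / 0.895 / 0.951
- 70% persisting: 0.730 / 0.739 / 0.758
- 40% persisting: 0.621 / 0.609 / 0.639

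These lie on both sides of 0.832.

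**The case against.** The strongest reply is that the affected figures belong to a model the trial does not use for its primary analysis. The planned model includes the baseline rate. If all of k persists between years, that model has 0.87–0.95 power at 20%, so the printed 0.832 would indeed be conservative for it. No text in the documents supports a particular year-specific fraction, and the plan describes k as between-community variation. This stands as a limit: nothing here shows that the planned analysis has less power than printed. It does not rescue the word conservative without qualification, because modest year-specific dispersion reverses the comparison and the documents do not report the year-to-year correlation that would settle it.

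Second, both documents say that the simulated analyses followed the planned analysis section except for the baseline covariate, and that section specifies small-sample adjusted SEs. On its face, the adjusted SE was used. Against that, the note to SAP Table 1 says only "Empirical SE estimates were utilized", and a null rate of 0.075 does not fit the adjusted SE. That the unadjusted SE was used is an inference. The text and the null row need reconciling either way.

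Third, community sizes are assumed and scaled to the very table in question, and SAP Table 3 was not recomputed. The exact magnitudes are therefore illustrative. The direction does not depend on the sizes, and power fell by several points for every size spread tried.

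Finally, the 40% target, the number of communities, the test and the estimate are unaffected, and the SAP records that results have been disseminated. All true. But the 83% sentence remains in both documents and bears on how a small or null effect is read.

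**Conclusion.** The concern holds. k = 0.0431 understates the dispersion of 12-month counts, and the power printed at reductions of about 19–25% is too high for the no-baseline model that was simulated. With the smallest correction, in which all dispersion persists, power falls from 0.792 to about 0.69–0.73 at 19%, from 0.832 to about 0.75–0.78 at 20%, and from 0.961 to about 0.91–0.93 at 25%. These sizes rest on assumed lognormal community sizes and the unadjusted SE that reproduces the table. Any year-specific dispersion lowers them further. Power at 40% remains above 0.99. For the planned baseline-adjusted analysis, the direction relative to the printed values is undetermined, so conservative is unsupported as an unqualified description.

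**What to change.** - Refit k with 2016 and 2017 as two single-year records per community and a community-level correlation. Two-year totals are not enough, because they restore only the Poisson part: with 30% year-specific dispersion they return 0.058–0.065, against 0.069–0.077 from single-year records.
- Re-run Protocol Table 12 and SAP Tables 1 and 3 with the planned small-sample adjusted SE, with and without the baseline-rate covariate, using the observed 2016–17 correlation. Show the null row in each table and state which SE was used.
- Restate the 83% sentence in both documents. Keep, qualify or remove the word conservative according to the result.

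The cost is one refit of an existing pilot model and a re-run of the simulation. The only downside is a stated power that may be less favourable. The 67 communities, the primary test and its estimate do not change.

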### 9.4 Statistical Analyses

#### 9.4.1 General Approach

The HCS is a multi-site, parallel arm, cluster randomized, wait-list controlled trial of Communities That HEAL (CTH). All statistical computations will be performed by HCS biostatisticians. For summaries of study data, categorical measures will be summarized in tables listing the frequency and the percentage of participating communities; continuous data will be summarized by presenting mean, standard deviation, median, 95% confidence intervals, and range; and ordinal data will be summarized by only presenting median and range. The balance or imbalance of these characteristics will be studied and reported, particularly for analyses comparing the two study groups. Graphical displays will be used to show distributions (box plots, density curves). The reported p-values will be based on two-sided tests at an  $\alpha=0.05$  unless otherwise specified and statistical models will generally be adjusted for the covariates in the randomization. No adjustment will be made for multiple testing for the primary analyses given there is a single primary outcome being compared between two arms. For the analysis and modeling of the data, general methodological standards will be followed throughout, including proper handling of missing data, assessing model assumptions, incorporating appropriate covariates, and conducting sensitivity analysis to assess robustness of findings. For continuous outcomes, checks of normality will be performed and if required, transformations or non-parametric tests will be employed. Additional details for potential covariate adjustments in secondary analyses or handling violations of analytic method assumptions will be detailed in the statistical analysis plan.

The analyses will be done using an ITT approach, including all randomized HCS communities according to assigned group. For the primary and secondary outcomes, every effort will be made to minimize missing data; however, in the event that missing data do exist, we will document the process that resulted in the missing data and consider model-based imputation methods to account for the missing data if needed. In short, guidelines for missing data in clinical trials prescribed by a National Research Council report, and guidelines for handling

missing data in cluster trials, will be followed. Additional details will be supplied in the statistical analysis plan.

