The previously described marginal negative binomial regression model will be fit utilizing PROC GLIMMIX in SAS (version 9.4 or higher). We note that GLIMMIX will utilize maximum likelihood theory to estimate parameters. However, in general, this procedure utilizes unbiased estimating equations for regression parameter estimation; therefore, quasi-likelihood theory or generalized estimating equation (GEE) theory applies. Specifically, we will utilize small-sample adjusted empirical standard error estimates and degrees of freedom equal to the number of communities minus the number of regression parameters. Furthermore, as a sensitivity analysis, a permutation test at the 0.05 significance level will be conducted with respect to the impact of the intervention. This test will be based on our implementation of constrained randomization.

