- b) Fit the model in GLIMMIX using the “empirical=root” option, and extracting estimated standard error,
- c) Calculate the average of the standard errors from steps a) and b),
- d) Calculate the t-statistic from the treatment effect value from step a) and divide it by the average standard error from step c),
- e) Assume the degrees of freedom for the t-statistic calculated in step d) is equal to number of communities (67 or 66) minus number of regression parameters (7), and calculate the p-value for the t-statistic from step d).

In the unlikely event this estimator is computationally infeasible, we will use one of the following SAS options: “empirical=FIRORES”, “empirical= FIROEEQ”, or “empirical =DF”.

The results of the model will be used to estimate and report:

- The adjusted relative rate (and 95% CI and p-value) of the rate of opioid OD deaths during the evaluation period between Wave 1 and Wave 2.
- The adjusted rate (and 95% CI) in the rate of opioid OD deaths during the evaluation period within Wave 1.
- The adjusted rate (and 95% CI) in the rate of opioid OD deaths during the evaluation period within Wave 2.

Note that adjusted rates and 95% CIs will be calculated using least squares means.

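### Table 12's powers come from a simulated test that rejects 7.5% of the time under no effect; at a true 5% level the simulated model has about 78% power for a 20% reduction, not 83%

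*Protocol*

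**What the plan says.** Protocol Section 9.2 bases power on a negative binomial simulation driven by pilot data from all 67 communities. It stresses the precision of the result: with 20,000 replications, "95% confidence intervals corresponding to our calculated power are no wider than 0.011" for powers of 0.80 or more. Table 12 gives 0.999 for a 40% reduction, 0.832 for a 20% reduction and, in its last row, 0.075 at relative risk 1.00. The text summarises this as more than 99% power at 40% and "at least 83% power for any reduction of 20% or more".

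The simulated analyses are said to follow Section 9.4.2, except that the baseline death rate "was not incorporated into the model as a covariate, thus providing conservative power estimates". For the planned analysis, Section 9.4.2 states: "we will utilize small-sample adjusted empirical standard error estimates", with degrees of freedom equal to communities minus regression parameters. SAP Section 6.2.1 makes this specific by fitting the model with two adjusted estimators: "Calculate the average of the standard errors from steps a) and b". The level is fixed in Protocol Section 9.4.1 ("The reported p-values will be based on two-sided tests at an" alpha of 0.05) and again in SAP Section 4.1.

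SAP Section 3.3 repeats the powers in its Table 1 but stops at the 19% row, so the 18% and 0% rows are missing. Its table note says "Empirical SE estimates were utilized", and the text again describes the approach as "thus providing conservative power estimates".

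**The concern.** At relative risk 1.00 the power column is the type I error rate of the simulated test. It reads 0.075 where 0.05 is intended. A test that rejects too often under the null also rejects too often under every alternative, so all the powers in the table are overstated as 5%-level figures. Neither document comments on the 0.075. Both call the powers conservative on the ground that a useful covariate was left out, while an error of known direction pushes the other way.

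What is at stake is the claim about effects smaller than the 40% target. Anyone judging how well the trial could detect a reduction of about 20% will rely on the 83% sentence. A reader of the SAP alone cannot see the problem, because the null row is not printed there. SAP Table 3, on community withdrawals, used the same method and also prints no null row.

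**Working it through.** **Inputs.** Table 12: 0.075 at relative risk (RR) 1.00, 0.832 at RR 0.80, and the other rows. Protocol 9.2: 20,000 replications, 67 communities, k = 0.0431, control probabilities 0.000255 to 0.000436. Protocol 9.4.1 and SAP 4.1: two-sided 0.05. Community sizes are not in the documents, and steps 1 to 5 do not need them.

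**1. Is 0.075 noise?** The standard error of a 5% rejection rate over 20,000 runs is √(0.05 × 0.95 / 20,000) = 0.00154. The distance is (0.075 − 0.05) / 0.00154 = 16.2 standard errors. The Monte Carlo 95% interval for 0.075 is 0.071 to 0.079.

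**2. Does the rest of the table behave like a 7.5% test?** Use power = Φ(|ln RR|/SE − c). The two-sided 7.5% critical value is c = Φ⁻¹(1 − 0.0375) = 1.780. One fitted SE of 0.0813 then reproduces the eight rows from 25% down to 18%:

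- predicted: 0.961, 0.945, 0.924, 0.899, 0.868, 0.833, 0.792, 0.746
- printed: 0.961, 0.943, 0.925, 0.899, 0.866, 0.832, 0.792, 0.748

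The root mean square error is 0.0014. With c = 1.960 the best fit gives 0.0049. Solved row by row at c = 1.780, the SE stays between 0.0810 and 0.0817. The null row is therefore unlikely to be a misprint.

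**3. Convert to a 5% test.** At RR 0.80 the noncentrality is 1.780 + Φ⁻¹(0.832) = 1.780 + 0.962 = 2.743 (unrounded terms). Power at c = 1.960 is Φ(2.743 − 1.960) = Φ(0.783) = 0.783. The same steps for the other rows give:

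| Reduction | Printed | At a 5% level |
|---|---|---|
| 18% | 0.748 | 0.687 |
| 19% | 0.792 | 0.737 |
| 20% | 0.832 | 0.783 |
| 21% | 0.866 | 0.823 |
| 22% | 0.899 | 0.864 |
| 25% | 0.961 | 0.943 |
| 40% | 0.999 | at least 0.998 |

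Interpolating between the corrected rows, 80% power is reached at 20 + (0.800 − 0.783)/(0.823 − 0.783) ≈ 20.4%. Power of 0.832 is reached at 21 + (0.832 − 0.823)/(0.864 − 0.823) ≈ 21.2%.

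**4. Sensitivity.** A t reference on 61 degrees of freedom (67 communities minus 6 parameters without the baseline rate) gives 0.781 at 20%. The ends of the Monte Carlo interval for the null row give 0.776 to 0.790. The shift of 0.832 − 0.783 = 0.049 compares with a stated precision of 0.011, which covers simulation error only.

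**5. What must the omitted covariate supply?** To bring the simulated model to 0.80 at a 20% reduction, it must cut the variance of the treatment estimate by 1 − (2.743/2.802)² = 4.2%, where 2.802 = 1.960 + 0.842. To restore 0.832 it must cut it by 1 − (2.743/2.922)² = 11.9%, where 2.922 = 1.960 + 0.962.

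**6. Likely cause, by simulation with assumed community sizes.** Sizes were lognormal, median 50,000 to 55,000, log-SD 1.3 to 1.5, with 6,000 replications and no baseline covariate.

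- Unadjusted empirical SE, normal reference: null rejection 0.075 to 0.081; power at RR 0.80 0.828 to 0.846.
- Averaged adjusted SE of SAP 6.2.1, t on 61 df: null rejection 0.048 to 0.049; power 0.764 to 0.785.
- Unadjusted SE with its critical value reset to true 5% size: power 0.770 to 0.786.

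Over a wider assumed range (median 40,000 to 60,000, log-SD 1.1 to 1.5, 3,000 replications) the adjusted test gave 0.71 to 0.79.

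**7. The planned model, again with assumed sizes** (lognormal, median 48,000, range 8,000 to 741,000). With the log baseline rate, averaged SE and 60 df (1,500 replications), power at RR 0.80 was 0.70, 0.77, 0.82 and 0.85 when 0%, 50%, 79% and 100% of between-community variation persists from baseline. Its size was 0.044 to 0.057. On the same sizes, the unadjusted test without the covariate gave 0.779 (3,000 replications).

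**The case against.** The strongest reply is that 0.78 is the power of no test that anyone will run. The simulated test had 0.832 at its own size. The planned test uses adjusted standard errors and 60 degrees of freedom, and adds the baseline death rate. Section 9.2 ties the word conservative to the omission of that covariate and hedges it by saying only that power may turn out higher. Step 7 shows that the planned test can exceed the table-style figure if baseline differences persist strongly. This stands as a limit: 0.78 corrects the simulated model only. It does not rescue the claim. Protocol 9.2 itself calls the influence of baseline rates unknown, and in step 7 the planned test falls below the table-style figure at 0% and 50% persistence. The net direction has not been shown.

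Other fair points: the protocol does print the 0% row, so it is undiscussed, not hidden. The cause is also unproven, because adjusted empirical errors are empirical errors too and the SAP table note does not separate the two. The conversion in step 3 does not depend on the cause.

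Finally, the 20% row did not set the number of communities, and the SAP records that results have already been disseminated. That limits the consequence, but the printed statement still needs correcting.

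**Conclusion.** The concern holds. The 83% for a 20% reduction is not a 5%-level power. For the model simulated, the corresponding figure is about 0.78, roughly 5 points lower, and the rows from 18% to 25% fall by about 2 to 6 points. This rests on the printed 0.075 and a normal approximation that reproduces the printed rows closely. The power of the planned test at 20% cannot be derived from the documents, because neither the community sizes nor the persistence of baseline rates is given. Under assumed sizes it ranged from 0.70 to 0.85. The description as conservative is therefore unsupported as it stands. Power above 99% for the 40% design target is unaffected. Nothing here shows inflated type I error in the planned test, whose simulated size was close to 5%.

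**What to change.** Rerun the simulation with the exact standard error and degrees-of-freedom rule of SAP Section 6.2.1 (communities minus fitted parameters), and print the 0% row. Restate the 83% sentence, Table 12 and SAP Table 1 at a verified 5% level. Rerun SAP Table 3 the same way, since SAP Section 6.2.5 says it used the Section 3.3 method. Keep the word conservative only if a run that includes the baseline death rate, over a stated range of baseline-to-evaluation correlation, supports it.

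The cost is a rerun of existing code and some rewording. The number of communities, alpha and the primary analysis do not change. The stated power at 20% falls by about 5 points for the simulated model.

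A separate point in the same sections: Protocol 9.4.2 plans a permutation test as a sensitivity analysis and SAP 6.2.5 does not list it. The two should be reconciled.
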